## **12.9. Echocardiogram**

An echocardiogram will be performed as specified in the SoA ([Table 3](#)). For patients enrolled in the study prior to Amendment 5 and irrespective of study schedule, after signing an updated informed consent, all patients should have a transthoracic echocardiogram at their next scheduled visit and then in conformity with the SoA ([Table 3](#)).

The echocardiogram will be interpreted locally by a cardiologist or designee for immediate safety evaluation. The echocardiograms will also be collected for centralized review and interpretation by a cardiologist.

## **12.10. Spinal X-ray**

A spinal X-ray will be performed at screening/baseline to rule out patients with severe scoliosis or those that would require major spinal surgical procedures during the 1-year study assessment period.

## **12.11. Pulmonary Exam**

Pulmonary examinations will be performed by a pulmonologist (or appropriate individual as per standard institutional practice) at the time points specified in the SoA ([Table 3](#)). Prior to trial entry, a pulmonologist (or appropriate individual as per standard institutional practice) will review and document ventilator usage in the 2 weeks prior to screening.

Patients may be fitted with a non-invasive positive pressure ventilator (e.g., bilevel positive airway pressure [BiPAP]) at the discretion of the pulmonologist and/or Investigator. Non-invasive ventilatory support equipment will be provided by AveXis through a third-party vendor if not covered by the patient's insurance.

Should the patient require non-invasive ventilator support at any time during the trial, the equipment to be provided must be approved by AveXis in order to ensure ability to upload usage data.

Patients requiring non-invasive ventilatory support will be asked to bring the machine to each study visit such that the study staff can remove the storage device which captures actual usage data. The hours per day usage data for each day between visits will be extracted with software provided by the device manufacturer into a format that will be transferred/transcribed to the clinical database.

## 12.13. Photographs of Injection Site

Photographs will be taken of the injection site at the time points specified in [Table 3](#) to monitor healing of the injection wound. The Day 1 injection site photograph will be performed prior to the start of gene replacement therapy injection. AveXis will provide a secure and confidential upload process for transfer and storage of the photographs from the investigative sites to a contracted third-party vendor that will compile and arrange photographs as per AveXis requirements. Any/all photographs received at AveXis or the contracted vendor will be treated as confidential study data and will be the sole property of AveXis. AveXis and the contracted vendor will provide this secure, encrypted transfer and storage solution to properly protect the identities of patients/families in the photographs, which may be shared with regulatory agencies, the medical community, and/or in appropriate venues to discuss the results of this clinical trial.

## 12.14. Laboratory Assessments

Biological samples will be collected throughout the trial at the time points specified in [Table 3](#). Biological samples will be collected and shipped to a central laboratory. Samples for laboratory tests required on the day prior to dosing (Day -1) will be collected prior to dosing and will be processed locally by the site's Clinical Laboratory Improvement Amendment (CLIA) -certified local laboratory. In some cases, samples may be collected locally due to a need for immediate results or other safety or logistical concerns.

**Table 7: Total Blood Volume**

Visit	Tests 	Total Volume (mL) 
Screening	Hematology, chemistry/CK-MB  or Troponin I, coagulation, virus serology, immunology sample (AAV9/SMN Ab only), diagnostic confirmation sample	19.3-19.6
Day -1	Hematology, chemistry, coagulation, capillary blood gas	6.0
Day 2	Hematology, chemistry, coagulation, capillary blood gas	6.0
Day 7	Hematology, chemistry/CK-MB or Troponin I, coagulation, immunology sample	10.0-12.3
Day 14	Hematology, chemistry, coagulation immunology sample	9.0-11.0
Day 21	Hematology, chemistry, coagulation immunology sample	9.0-11.0
Day 30	Hematology, chemistry/CK-MB or Troponin I, coagulation, immunology sample	11.0-12.3
Day 44	Chemistry	1.3
Day 60	Hematology, chemistry/CK-MB or Troponin I, coagulation	6.0-6.3
Day 72	Chemistry	1.3

Visit	Tests 	Total Volume (mL) 
Month 3	Hematology, chemistry, coagulation	5
Month 4	Hematology, chemistry, coagulation	5
Month 5	Hematology, chemistry, coagulation	5
Month 6	Hematology, chemistry/CK-MB or Troponin I, coagulation	6.0-6.3
Month 7	Hematology, chemistry, coagulation	5
Month 8	Hematology, chemistry, coagulation	5
Month 9	Hematology, chemistry/CK-MB or Troponin I, coagulation	6.0-6.3
Month 10	Hematology, chemistry, coagulation	5
Month 11	Hematology, chemistry, coagulation	5
Month 12	Hematology, chemistry/CK-MB or Troponin I, coagulation	6.0-6.3
Last Study Visit (Month 15) 	Hematology, chemistry/CK-MB or Troponin I, coagulation	6.0-6.3
Total Volume for Study 1-Year Duration		137.9-147.3

Immunology = Serum antibody to AAV9 and SMN, IFN- $\gamma$  ELISpot to detect T-cell responses to AAV9 and SMN

 Immunology sample requires 4-6 mL of whole blood

 Maximum total blood volume specified for each visit; in cases where tests can be combined, lower blood volumes may be sufficient. Positive serology samples at screening and elevated T-cell responses at Day 30 may require additional surveillance samples not reflected in the table.

 Troponin I will be measured instead of CK-MB in new patients who are screened and enrolled after amendment 5 (protocol version 6.0) goes into effect. Participants who have been screened and enrolled but who have not yet received gene replacement therapy (visit #2) at the time that amendment 5 (protocol version 6.0) goes into effect will have baseline troponin I testing prior to treatment with AVXS-101, and will have troponin I testing in place of CK-MB. CK-MB will be collected from all other participants.

 Only patients enrolled in Cohort 3 will have a month 15 visit. Patients enrolled in Cohorts 1 and 2 will complete the study or have EOS visit at Month 12

In a case where sufficient blood cannot be collected from a patient, blood will be used in the following priority order with the first having greatest priority and last having the least priority:

1. Safety blood labs: chemistry → hematology → coagulation → creatinine kinase isozyme-MB (CK-MB) or troponin
2. Interferon gamma (IFN- $\gamma$ ) ELISpot to detect T-cell responses
3. Serum antibody to AAV9 and SMN
4. Genetic re-confirmation testing

If there is not sufficient blood volume to include the genetic reconfirmation testing sample at the screening visit, the patient must return before the inpatient period. All patients must have genetic reconfirmation testing completed.

### **12.14.1. Hematology**

Hematology analysis will include a CBC with differential and platelet count with smear. Samples will be collected and shipped in accord with the laboratory manual provided by the central laboratory as per the time points specified in [Table 3](#).

Immediate/same-day hematology analyses required during in-patient dosing, as determined by the Investigator, will be performed as per investigational site standard procedures at the local laboratory.

### **12.14.2. Serum Chemistry**

Samples will be collected and shipped in accord with the laboratory manual provided by the central laboratory as per the time points specified in [Table 3](#).

Immediate/same-day chemistry analyses required during in-patient dosing, as determined by the Investigator, will be performed as per investigational site standard procedures at the local laboratory.

Chemistry analysis will include the following at all study visits:

- Serum GGT
- AST/ALT
- Serum total bilirubin
- Direct bilirubin
- Albumin
- Glucose
- Total creatine kinase
- Creatinine
- BUN
- Electrolytes
- Alkaline phosphatase

CK-MB or troponin I will be collected as specified in the SoA ([Table 3](#)). Troponin I will be measured instead of CK-MB in new patients who are screened and enrolled after amendment 5 (protocol version 6.0) goes into effect. Participants who have been screened and enrolled but who have not yet received gene replacement therapy at the time that amendment 5 (protocol version 6.0) goes into effect will have baseline troponin I testing prior to treatment with AVXS-101 and will have troponin I testing in place of CK-MB. CK-MB will be collected from all other participants.

Investigators will receive laboratory results from all study visits from the central laboratory (except Day -1).

### **12.14.3. Virus Serology**

The administration of an AAV vector has the risk of causing immune-mediated hepatitis. For patients who have HIV or positive serology for hepatitis B or C or Zika virus, administration of AAV vector may represent an unreasonable risk; therefore, negative serology testing must be confirmed at screening, prior to treatment. These samples will be collected and shipped in accord with the laboratory manual provided by the central laboratory.

### **12.14.4. Coagulation Studies**

Coagulation studies include prothrombin time, partial prothrombin time, and international normalized ratio will be collected in accordance with the laboratory manual provided by the central laboratory. Coagulation studies will be performed as per the timepoints specified in [Table 3](#).

### **12.14.5. Urinalysis**

Urine samples will be collected in accord with the laboratory manual provided by the central laboratory as per the time points specified in [Table 3](#).

Day -1 and immediate/same-day urinalyses required during in-patient dosing, as determined by the Investigator, will be performed as per investigational site standard procedures at the local laboratory.

Urinalysis will include the following parameters:

- Color
- Clarity/turbidity
- pH
- Specific gravity
- Glucose
- Ketones
- Nitrites
- Leukocyte esterase
- Bilirubin
- Blood
- Protein
- Red Blood Cells
- WBCs
- Squamous epithelial cells
- Casts
- Crystals

- Bacteria
- Yeast

#### **12.14.6. Capillary Blood Gas**

Capillary blood gas will be completed as per the time points specified in [Table 3](#). A puncture or small incision will be made with a lancet or similar device into the cutaneous layer of the patients' skin at a highly vascularized area (heel, finger, toe). To accelerate blood flow and reduce the difference between the arterial and venous gas pressures, the area will be warmed prior to the puncture. As the blood flows freely from the puncture site, the sample will be collected in a capillary tube.

#### **12.14.7. Research Immunology Blood**

##### **12.14.7.1. ELISA: Anti-AAV9 Ab**

Blood samples will be collected and shipped to the central laboratory in accord with the laboratory manual to test for serum antibodies to AAV9 as per the timepoints specified in [Table 3](#).

##### **12.14.7.2. ELISA: Anti-SMN Ab**

Blood samples will be collected and shipped to the central laboratory in accord with the laboratory manual to test for serum antibodies to SMN as per the timepoints specified in [Table 3](#).

##### **12.14.7.3. IFN- $\gamma$ ELISpot**

Blood will be collected and shipped to the central laboratory in accord with the laboratory manual to perform IFN- $\gamma$  ELISpot to detect T-cell responses to AAV9 and SMN as per the timepoints specified in [Table 3](#).

#### **12.14.8. Baseline Screening of Biological Mother**

There is potential that the biological mother of the enrolled patient may have pre-existing antibodies to AAV9 that may be transferred to the patient via placental transfer in utero or theoretically through breast milk. Informed consent will be requested from the biological mother of the patient to screen the biological mother for circulating antibodies to AAV9. Once informed consent has been obtained, the biological mother will have her blood drawn from a peripheral vein and shipped to the central laboratory for screening of anti-AAV9 antibodies.

If AAV9 antibodies are identified, the Investigator should discuss with the biological mother whether to continue or to stop breastfeeding.

Patients consuming banked breast milk from donor sources that cannot be tested for anti-AAV9 antibodies must be transitioned to formula prior to participation.

#### **12.14.9. Blood for Diagnostic Confirmation Testing**

A blood sample will be collected during the screening visit and shipped to the central laboratory in accord with the laboratory manual for re-confirmation of *SMN1* deletions, *SMN2* copy

number, and absence of exon 7 gene modifier mutation (c.859G>C). This will be done to ensure consistency in diagnostic testing practices.

#### **12.14.10. Saliva, Urine, and Stool Collection**

Studies have shown that some vector can be excreted from the body for up to a few weeks after injection; this is called “viral shedding”. Vector shedding can be found in the blood, urine, saliva, and stool for up to a week following injection. The risks associated with the shed vector are not known at this time; however, it is unlikely as the vector is non-infectious and cannot replicate. Regardless, IRB-approved instructions should be provided to patient families and care givers regarding use of protective gloves if/when coming into direct contact with patient bodily fluids and/or waste as well as good hand-hygiene for a minimum of four weeks after the injection.

Additionally, patients are prohibited from donating blood for two years following the vector injection.

Saliva, urine, and stool samples will be collected in accord with the laboratory manual for viral shedding studies in accord with [Table 3](#). Patients at all sites  $\geq$  48 months of age who are no longer in diapers will provide full volume urine and full volume feces samples at the timepoints specified in the SoA ([Table 3](#)) for at least one void and one defecation. Samples will be prepared as per the laboratory manual, stored in a -80 freezer, and shipped to the central laboratory in accord with the laboratory manual.

A subset of patients at sites opting to participate in the viral shedding sub-study will have 24-hour total volume urine and fecal samples collected through 24 hour-post dose and 48 hours-post dose (to include all excretions in those time periods).

## 13. ADVERSE AND SERIOUS ADVERSE EVENTS

### 13.1. Definition of Adverse Events

#### 13.1.1. Adverse Event

An AE is the development of an undesirable medical condition or the deterioration of a pre-existing medical condition following or during exposure to a pharmaceutical product, whether or not considered causally related to the product. In clinical studies, an AE can include an undesirable medical condition occurring at any time, including baseline or washout periods, even if no study treatment has been administered.

All AEs that occur after any patient has received treatment, during treatment or up through the last study visit, whether or not they are related to the study, must be recorded on forms provided by Syneos Health, formerly INC (a Contract Research Organization responsible for managing specific aspects of the study, as designated by AveXis).

All AEs will be classified in accordance with the CTCAE version 4.03 outlined in [Table 6](#).

Study enrollment will be interrupted should any patient experience an unanticipated CTCAE Grade 3, or higher AE toxicity that is possibly, probably or definitely related to the product. The event will then be reviewed by the DSMB/DMC and an evaluation will be made as to whether the study should be terminated early following the discontinuation rules.

Unanticipated CTCAE Grade 3 or higher AEs that are possibly, probably or definitely related to gene replacement therapy must be reported within 24 hours to AveXis and/or designee to ensure timely escalation to the DSMB/DMC.

#### 13.1.2. Serious Adverse Event

An SAE is an AE occurring during any study phase (i.e., baseline, treatment, washout, or follow-up), and at any dose of the investigational product, comparator or placebo, that fulfils one or more of the following:

- Results in death
- It is immediately life-threatening
- It requires in-patient hospitalization or prolongation of existing hospitalization
- It results in persistent or significant disability or incapacity
- Results in a congenital abnormality or birth defect
- It is an important medical event that may jeopardize the patient or may require medical intervention to prevent one of the outcomes listed above

All SAEs that occur after any patient has been enrolled, before treatment, during treatment, or up through the last study visit, whether or not they are related to the study, must be recorded on forms provided by Syneos Health.

### 13.1.3. Other Adverse Event

The following specific treatment-emergent AEs of special interest (AESIs), which may be searched using Standardized MedDRA queries, will be summarized:

- Elevated liver enzymes

Grade 3 or higher elevated liver enzyme events related to AVXS-101 must be collected and recorded on forms provided by the Contract Research Organization. These events should be reported within 24 hours of occurrence, whether or not they are deemed to be an SAE.

Other adverse events (OAEs) could be identified by the Drug Safety Physician and, if applicable, also by the Clinical Trial Team Physician during the evaluation of safety data for the Clinical Study Report. Examples of AESIs include hepatotoxicity, cardiac toxicity, and thrombocytopenia. Significant AEs of particular clinical importance, other than SAEs and those AEs leading to discontinuation of the patient from the study, will be classified as OAEs. For each OAE, a narrative may be written and included in the Clinical Study Report.

### 13.2. Relationship to Study Product

An Investigator who is qualified in medicine must make the determination of relationship to the investigational product for each AE (unrelated, possibly related, probably related or definitely related). The Investigator should decide whether, in his/her medical judgment, there is a reasonable possibility that the event may have been caused by the investigational product. If no valid reason exists for suggesting a relationship, then the AE should be classified as “unrelated.” If there is any valid reason, even if undetermined, for suspecting a possible cause-and-effect relationship between the investigational product and the occurrence of the AE, then the AE should be considered “related.” If the relationship between the AE/SAE and the investigational product is determined to be “possible” or “probable” the event will be considered to be related to the investigational product for the purposes of expedited regulatory reporting.

### 13.3. Recording Adverse Events

Adverse events spontaneously reported by the patient or family and/or in response to an open question from the study personnel or revealed by observation will be recorded during the study at the investigational site. However, abnormal values that constitute an SAE or lead to discontinuation of administration of study product must be reported and recorded as an AE. Information about AEs will be collected from the time of IT injection until the end of the study. Serious adverse event information will be collected from signing of consent form until the last study visit. The AE term should be reported in standard medical terminology when possible. For each AE, the Investigator will evaluate and report the onset (date and time, if start date during inpatient period), resolution (date and time, if start date during inpatient period), intensity, causality, action taken, serious outcome (if applicable), and whether or not it caused the patient to discontinue the study.

Intensity will be assessed according to [Table 6](#) in [Section 13.1.1](#).

It is important to distinguish between serious and severe AEs. Severity is a measure of intensity whereas seriousness is defined by the criteria under [Section 13.1.2](#). An AE of severe intensity may not be considered serious.

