Nonclinical cardiovascular toxicity findings that could potentially be relevant to the clinical use of AVXS-101 have been reported in 2 mouse toxicology studies of AVXS-101. Similar findings were reported in both studies. Findings in the ventricles of the heart were comprised of inflammation, edema and fibrosis. Primary findings in the atrium of the heart were thrombosis and inflammation. The underlying mechanism of these findings and the translatability of the observed findings in mice to primates are not known at this time.

The available clinical cardiovascular safety data have not provided evidence for a cardiovascular safety problem in humans. As of the last update to the Investigator's Brochure (v5), there have

been no cardiovascular AEs that have been judged to be related to AVXS-101 in the clinical studies.

A transient decrease in platelet counts has been observed with both IV and less frequently with IT administration. The majority of values remained above the lower limit of normal. Decreases were clinically asymptomatic and transient.

This risk can be effectively managed through monitoring platelet counts for 1 month following dosing, and appropriate prednisolone (or an equivalent corticosteroid in countries where prednisolone is not available) use.

Preclinical data indicate that in most cases, DNA delivered by recombinant AAV vectors predominantly persists as extrachromosomal elements (episomes) rather than integrating into host cell genomes ([McCarty 2004](#)). Although AVXS-101 is also not anticipated to integrate into the host cell genome as described above, the long-term consequences of administering AAV viral vectors to humans are not yet fully understood. This is in contrast to wtAAV, also nonpathogenic, which has the ability to stably integrate into the host cell genome at a specific site (designated AAVS1) in the human chromosome 19 ([Kotin 1990; Surosky](#) ). Since the AVXS-101 product uses AAV9 with all of the wtDNA removed from the capsids, except for the inverted terminal repeats (ITRs), the potential risk of incorporation of AVXS-101 into the patient chromosomal DNA is thought to be significantly reduced.

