## **7.4. Dose Adjustment Criteria**

The study investigates a one-time IT injection of AVXS-101; therefore, no dose adjustments are possible.

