## **9.3. Treatment Compliance**

AVXS-101 will be administered as a one-time IT injection.

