## 10.7. Dose Escalation

There will be a 4-week dosing interval between all patients within Cohort 1 to allow review of the safety analysis from six-time points (Days 1, 2, 7, 14, 21, 30) prior to dosing of the next patient.

AveXis will confer with the DSMB/DMC on all Grade III or higher AEs within approximately 48 hours of awareness that are possibly, probably or definitely related to the study agent before continuing enrollment. Safety data will be reviewed by the DSMB/DMC during quarterly meetings; following enrollment of the first three patients  $\geq 6$  months and  $< 24$  months of age at the time of dosing and based upon the available safety data a decision will be made whether to: a) stop due to toxicity, or b) proceed to Cohort 2 using Dose B.

Should the determination be made to advance to Cohort 2 (Dose B), again there will be at least a 4-week interval between dosing of the first three patients  $< 60$  months of age at the time of dosing within the cohort. Based on the available safety data from the first three Cohort 2 patients and all of the Cohort 1 patients, the DSMB/DMC may decide and document during quarterly meetings that further 4-week intervals between patients dosing is unnecessary. AveXis will take this recommendation into consideration and will make the final determination whether to persist with 4-week intervals between patients dosing going forward. The decision will be communicated to sites and IRBs in a formal sponsor letter. AveXis will confer with the DSMB/DMC on all Grade III or higher AEs within approximately 48 hours that are possibly, probably or definitely related to the study agent before continuing enrollment. Safety data will be reviewed by the DSMB/DMC during quarterly meetings; following enrollment of the first six patients and based upon available safety data, a decision will be made whether to a) stop due to toxicity or b) continue to enroll an additional 21 patients until 12 patients  $\geq 6$  months and  $< 24$  months of age at time of dosing and 12 patients  $> 24 < 60$  months of age at time of dosing have received Dose B.

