#### **4.4. Primary Safety Endpoints**

The primary safety endpoints are as follows:

- Any AE
- Any serious AE
- Any AE related to study product
- Any AE with CTCAE Grade  $\geq$  Grade 3

An AE is the development of an undesirable medical condition or the deterioration of a pre-existing medical condition following or during exposure to a pharmaceutical product, whether or not considered causally related to the product. AEs spontaneously reported by the patient or family and/or in response to an open question from the study personnel or revealed by observation will be recorded during the study at the investigational site. However, abnormal values that constitute a Serious Adverse Event (SAE) or lead to discontinuation of administration of study product must be reported and recorded as an AE. Information about AEs will be collected from the time of intrathecal injection until the end of the study. SAE information will be collected from signing of consent form until the last study visit.

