#### **11.3.2.4. Adverse Events of Special Interest**

The following specific TEAEs of special interest, which are primarily defined by using Standardized MedDRA queries (SMQ), will be summarized:

- Hepatotoxicity, identified via the following SMQ:
  - Hepatic disorders (SMQ)
- Thrombocytopenia, identified via the following CMQ:
  - Transient thrombocytopenia (CMQ)
- Cardiac events, identified via the following SMQs:
  - Ischemic heart disease (SMQ)
  - Cardiomyopathy (SMQ)
  - Cardiac arrhythmias (SMQ)

- Embolic and thrombotic events (SMQ)
- Myocardial infarction (SMQ)
- Thrombotic microangiopathy, identified via the following approach:
  - Criteria #1: cases with **any one** of the following PTs: thrombotic microangiopathy **OR** haemolytic uraemic syndrome **OR** atypical haemolytic uraemic syndrome
  - Criteria #2: cases with **at least one PT** from **EACH** of the following SMQs representing thrombocytopenia, hemolysis and relevant renal events respectively:
    - Haematopoietic thrombocytopenia (SMQ)
    - Haemolytic disorders (SMQ)
    - Acute renal failure (SMQ) **OR** Renovascular disorders (SMQ)
- Sensory abnormalities suggestive of ganglionitis, identified via the following CMQ:
  - DRG Cell Inflammation (CMQ)

For each AE of interest category, the number and percentage of patients experiencing at least one TEAE in the search for the event of interest will be presented overall and by actual dose received and age group. AEs of interest will be summarized by SOC and PT overall, by actual dose received, and age group.

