For hemoglobin and the liver function enzyme (LFE) tests of ALT, AST, and alkaline phosphatase, the number and percentage of patients in each age/dose group with a maximum CTCAE Grade of 1, 2, 3, or 4 (as defined by the central laboratory and based on CTCAE v4.03) at any post-baseline visit (regardless of the baseline value) through the end of study will be summarized. All LFE tables will include summary rows for the number and percentage of patients with at least Grade 2 and at least Grade 3 laboratory abnormalities. The hemoglobin table will include a summary row for the number and percentage of patients with a Grade 3 laboratory abnormality. Accompanying listings of all ALT, AST, total serum bilirubin, direct bilirubin, and alkaline phosphatase will be created for any patients who had at least a Grade 3 ALT, AST, or alkaline phosphatase value. A listing of hematology results will be provided for patients with hemoglobin abnormalities.

The number and percentage of patients meeting the following criteria will be summarized overall and by dose and age group:

- ALT >3x ULN, ALT >5x ULN, ALT >10x ULN, ALT >20x ULN
- AST >3x ULN, AST >5x ULN, AST >10x ULN, AST >20x ULN
- ALT or AST >3x ULN, ALT or AST >5x ULN, ALT or AST >8x ULN, ALT or AST >10x ULN, ALT or AST >20x ULN
- Total bilirubin >2x ULN, Total bilirubin >3x ULN
- ALT or AST >3x ULN and Total bilirubin >2x ULN
- ALT or AST >3x ULN and Total bilirubin >2x ULN and Alkaline phosphatase  $\geq$ 2x ULN
- ALT or AST >3x ULN and Total bilirubin >2x ULN and Alkaline phosphatase <2x ULN

A patient or event will be counted if the post-baseline laboratory values meet the above criteria regardless of the baseline laboratory value (i.e., the post-baseline laboratory value does not need to be worse than the baseline laboratory value). For the last three combination categories, the values do not need to have been collected at the same assessment. For patients meeting any elevation criterion, a corresponding listing of all ALT, AST, alkaline phosphatase, and total, direct, and indirect bilirubin values will be provided.

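### Outside liver enzymes, nothing requires a non-serious Grade 3 laboratory value to be recorded as an AE, because one of the recording rule's two triggers cannot occur after a single injection

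*Protocol*

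**What the plan says.** Protocol 13.3 records AEs that are volunteered, elicited by an open question or revealed by observation. It then sets the mandatory cases for laboratory results: "abnormal values that constitute an SAE or lead to discontinuation of administration of study product must be reported and recorded as an AE". SAP 4.4 repeats the rule under the primary safety endpoints, ending with values that "lead to discontinuation of administration of study product must be reported and recorded as an AE". Protocol 13.3 also notes that a severe event need not be serious.

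Treatment is a single dose. Protocol 9.3 states that "AVXS-101 will be administered as a one-time IT injection", and Protocol 7.4 that "The study investigates a one-time IT injection of AVXS-101; therefore, no dose adjustments are possible".

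Two other passages require or ask for recording of non-serious events. Protocol 13.1.3 requires related Grade 3 or higher liver-enzyme events to be recorded and reported within 24 hours, serious or not. Protocol 9.2.2 asks that an event prompting corticosteroids after the prednisolone taper be documented as an AE. Protocol 13.1.3 gives cardiac toxicity and thrombocytopenia as examples of special-interest events but attaches no recording rule to them.

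Protocol 5.5 describes transient platelet falls as a known effect, with most values above the lower limit of normal: "Decreases were clinically asymptomatic and transient".

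**The concern.** The second trigger is empty for any post-dose value, so the explicit obligation reduces to SAEs. An asymptomatic platelet fall is the kind of finding that a family will not volunteer and that may not meet an SAE criterion. Yet the measures that describe a dose's safety are counts of recorded AEs. The same Grade 3 value could count as an event when one investigator records it and not when another leaves it in the laboratory data. Protocol 14.7.1.2 and 15.1 take the escalation and expansion decisions after three children in a cohort, so one event more or less changes the apparent safety of a dose.

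Protocol 13.1.3 already separates recording from seriousness for liver enzymes. The question is why the other analytes that the programme watches are handled differently.

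**Working it through.** The documents give no figure to reproduce. The check is to follow one hypothetical result, a non-serious Grade 3 platelet value that the investigator does not record as an AE, through each place where safety is counted.

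| Place | What it works on | Is the value captured? |
|---|---|---|
| Primary safety endpoint (Protocol 14.7.1.1, SAP 4.4) | Recorded AEs: any, serious, related, Grade 3 or higher | No |
| Dose-limiting toxicity (Protocol 12.1.1) | Related Grade III AEs | No |
| Sponsor contact with the DSMB (Protocol 7.1, 10.7) | Related Grade III or higher AEs | No |
| Special-interest searches (SAP 11.3.2.4) | Coded treatment-emergent AE terms | No |
| Enrollment halt and ad hoc DSMB meeting (Protocol 7.5, 12.1.2, 15) | Unanticipated, related Grade 3 or higher events with symptoms or treatment; an important laboratory finding is included | Uncertain |
| Quarterly DSMB review (Protocol 15, SAP 13) | All available safety data; a database extract | Yes, but at the next meeting |
| PCS and shift tables (SAP 11.4.1, 11.4.2) | Laboratory values | Yes, but not isolated as Grade 3 or higher |
| Maximum-CTCAE-grade tables (SAP 11.4.2) | Four named analytes | No |

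Notes on the rows:

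1. **48-hour contact.** Protocol 10.7 says "AveXis will confer with the DSMB/DMC on all Grade III or higher AEs within approximately 48 hours of awareness", limited to events at least possibly related. Recording is necessary for contact but not sufficient.
2. **Halt and ad hoc rules.** No threshold defines an important laboratory finding. The lead sentences also require the event to be unanticipated. The halt sentences in 7.5 and 12.1.2 ask for symptoms and treatment; section 15 asks for symptoms and/or treatment. An asymptomatic, untreated platelet fall of a kind already described in 5.5 could fail these tests.
3. **PCS and shift tables.** PCS criteria are generally set at CTCAE Grade 2 or higher and are kept outside the SAP. Shift tables use low, normal and high. Neither separates Grade 3.
4. **Grade tables.** They are specified "For hemoglobin and the liver function enzyme (LFE) tests of ALT, AST, and alkaline phosphatase". Total bilirubin has separate rows by multiples of the upper limit of normal. Platelets and GGT have no table by grade or by multiple of the limit.
5. **Thrombotic microangiopathy search.** Criterion 1 needs one diagnostic term. Criterion 2 needs at least one coded term from each "of the following SMQs representing thrombocytopenia, hemolysis and relevant renal events respectively". If the pattern appears only in laboratory values and no criterion 1 term was reported, the search does not find it.

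Size of one unrecorded event, as incidence of Grade 3 or higher AEs, if that child has no other such AE and no other child in the group has one:

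- Cohort 1, or the first three children at Dose B or C: 1/3 = 33% becomes 0/3 = 0%.
- The four children treated at Dose C (SAP 2.2.1): 1/4 = 25% becomes 0/4 = 0%.
- The planned 12 per age group at Dose B: 1/12 = 8.3% becomes 0/12 = 0%.

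The effect therefore matters most in the groups of three or four.

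**The case against.** The strongest reply is that the rule sets a minimum. Protocol 13.1.1 requires all AEs after treatment to be recorded and graded, and 13.3 admits events revealed by observation. The grading table in 12.1.1 treats purely diagnostic observations as Grade 1 and medically significant events as Grade 3. Investigators receive the central laboratory results (12.14.2). Laboratory changes are also a safety criterion of their own in the synopsis.

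Much of this stands. A reader might infer that non-serious laboratory values are barred from being AEs; they are not. These passages permit recording, but none says which laboratory value must be treated as an AE, so the decision stays with the investigator.

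A reader might also infer that the DSMB has no laboratory route, or that the values vanish from the analysis. Protocol 7.5, 12.1.2 and 15 do name laboratory findings, quarterly review covers all safety data, and the SAP tabulates PCS values and shifts. These routes are slower, undefined or not graded, but they exist. SAP 13 adds that the SAP's safety analyses are not planned for the DSMB, which works from the extract.

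A third tempting inference is that a delay from 48 hours to a quarterly meeting exposes three more children (about 13 weeks / 4 weeks). The documents do not support this. In a group of three, at most 3 - 1 = 2 children remain after the first, and a DSMB review follows. Protocol 10.7 says the Cohort 1 interval exists so that data from six time points can be reviewed before the next dosing. In the Dose B expansion the interval may be waived, so 4 weeks is not a fixed spacing.

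**Conclusion.** The point holds as a gap in the recording rule. One of its two triggers cannot occur. Outside the liver-enzyme and post-taper corticosteroid provisions, recording a non-serious Grade 3 or higher laboratory value is discretionary, and four AE-based safety measures inherit that discretion. One event moves the apparent Grade 3 or higher incidence by 33 percentage points in a group of three and by 25 points at Dose C.

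This assumes that such a value occurs, is not serious and is not recorded at the investigator's discretion. The documents give no rate for any of these. The DSMB charter, case report form guidance, laboratory manual and PCS criteria are not in the documents and could narrow the gap. I would class this as a cheap improvement.

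**What to change.** **Protocol 13.3 and SAP 4.4.** Replace the discontinuation trigger with this rule: any new or worsened post-dose laboratory value of CTCAE Grade 3 or higher is recorded as an AE, whether or not serious. This is the grade the protocol already uses for its safety rules. Reconcile the new text with 7.5, 12.1.2, 13.1.3 and 15, which differ in how they treat laboratory findings, symptoms and treatment.

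**SAP 11.4.2.** Add platelets and GGT to the maximum-CTCAE-grade tables, and total bilirubin by grade beside its existing rows. Add a listing of all Grade 3 or higher laboratory values with no matching AE. SAP 11.4.2 mentions grades from the central laboratory only for the analytes now tabulated, so confirm that grades are available for the others.

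**Timing and cost.** The sponsor has decided to end the study early (SAP 2.2.1), so new recording wording may come too late for most events. The SAP outputs use data already collected and remain useful. The cost is one wording change in each document and two outputs. The downside is more AE records, a somewhat higher reported Grade 3 or higher incidence, and a few more DSMB contacts.
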